8.3 SUSAR reporting

The Sponsor (through its appointed CRO) will be responsible for the reporting of SUSARs to regulatory authorities. The Sponsor will follow the procedure detailed in the current version of the document “Detailed guidance on the collection, verification and presentation of adverse reaction reports arising from clinical trials on medicinal products for human use” available at EMEA website.

All suspected unexpected serious adverse reactions (SUSAR) will be reported in accordance with current regulations on clinical trials in Europe, to the competent authority and ethics committees and investigators within the time and procedure established by the “Detailed guidance on the collection, verification and presentation of adverse reaction reports arising from clinical trials on medicinal products for human use” and following any local regulations.

Terms of SUSAR Expedited Notification to Regulatory Authorities

The maximum period for reporting shall be 15 calendar days from first knowledge by the Sponsor of the suspected adverse reaction. When the suspected serious unexpected adverse reaction is fatal or life-threatening, the Sponsor shall notify within a maximum of 7 calendar days from first knowledge by the Sponsor of the case. This information must be completed as far as possible within eight additional calendar days. This information should include an assessment of the importance and implication of the findings, including relevant previous experience with the same or similar medication.

Expedited Reporting, Other Relevant Safety Information

The Sponsor shall notify (as soon as possible and no later than 15 days) any information which would alter the risk/benefit of the investigational drug, or to determine changes in dosage schedule or conduct of trial, for example:

- A qualitative change or an increase in the percentage of occurrence of the SAR expected, it is considered clinically significant.
- The SUSAR occurring after completion of a clinical trial reported by the investigator to the Sponsor.

New information concerning the conduct of the trial and likely to affect the safety of subjects, should be reported, including:

- Serious adverse events that may be associated with the test procedures and can modify the performance thereof.
- A significant risk to subjects such as lack of efficacy of the investigational drug used to treat a life threatening illness.
- Relevant safety new findings from animal studies (as formation of cancer).
- Any premature termination or temporary closure of a clinical trial with the same investigational drug for safety reasons, made in another country and by the same Sponsor.
- The Severe Adverse Reaction related solely to non-IMP considered relevant (as they are not subject to the general rules for expedited reporting of individual cases of SUSAR).

Furthermore, if relevant information is obtained, it will be notified as soon as possible.

Notification to Investigators

The Sponsor shall report the investigators any information that may affect the safety of trial subjects, as soon as possible. In addition, the Sponsor shall inform the researchers of the safety issues that impact the conduct of the clinical trial.

9. DATA MANAGEMENT

9.1 Electronic case report form (e-CRF)

In this protocol the term electronic case report form (e-CRF) refers to a web-based electronic data record in which the patient data will be collected.

An e-CRF is required to be completed by each participating site for each recruited patient. Only duly authorized and trained staff of each center will be granted access to enter and modify data in the e-CRF. Staff in charge of e-CRF usage will be given a unique user name and password.

The completed original electronic CRF files are the sole property of the Sponsor and should not be made available in any form to third parties, except for authorized representatives of the Sponsor or regulatory authorities, without written permission from the Sponsor.

The investigators have the ultimate responsibility for the collection and reporting of all clinical, safety and laboratory data entered on the e-CRFs and any other data collection forms (source documents) and ensuring that they are accurate, authentic, attributable, complete, consistent, legible, timely, enduring and available when requested. The e-CRF must be signed electronically by the investigator or by an authorized staff member to attest that the data contained in the e-CRF is true. Any changes to entries made in the e-CRF will be tracked by an audit trail system that will identify the old and new values of the data fields, the person who made the change and the reason of modification (if necessary), thus not obscuring the original entry.

The data will be recorded in the e-CRF GCP-compliantly at the study center. The e-CRF application (FDA and EMEA compliant) is designed to be entirely server-based. All stages in the processing, with the exception of the actual data entry and display, are performed centrally on a web/database server. All the data will be stored in the central server. The server will be securely housed at a professional hosting provider hired by the study CRO in Spain, guaranteeing effective security and backup mechanisms.

For data entry and print-outs, the e-CRF system is based fully on the so-called "web interface". Entry forms and reports are displayed on the client computer as HTML pages via any Web browser (IE 6+, FireFox 2+, Chrome, Safari 3+). No additional software is necessary to operate the e-CRF on the investigator's client computer (no plugin installations or software/hardware adaptations needed). The e-CRF is operating system independent (Win/Mac).

The data will be checked for correctness by validity and consistency checks. Implausible or missing data can be corrected or supplemented following discussion with the investigator. All corrections will be tracked and stored by the audit trail system.

Other than the investigator, only expressly authorized persons trained for the study may complete the e-CRF. Access control will be implemented by an auditable registry of user logins and logouts. Automatic session logouts will be implemented after predefined periods of inactivity for security reasons. The e-CRF will not show patient personal identification data (each subject will be identified by a unique trial number only).

A comprehensive Data Management Plan will be developed by the study CRO specifying e-CRF/Database design and data-related procedures and policies.

9.2 Record keeping

To permit evaluations, audits and/or inspections from regulatory authorities or the Sponsor, investigators agree to keep records, including the identity of all participating patients (e.g. enough information to link records), all original signed informed consent documents, safety reporting forms, source documents and appropriate documentation of relevant correspondence (e.g. letters, meeting minutes, telephone call reports). The records should be kept by the investigator according to International Conference on Harmonisation (ICH) and local regulations. In case an investigator becomes unable for any reason to continue the retention of study records for the required period, the Sponsor should be prospectively notified. The study records must be transferred to a designee acceptable to the Sponsor. Investigators must receive the Sponsor's written permission before disposing of any records.

10. MONITORING

The study will be monitored by regular onsite visits (two monitoring visits during the study and one closing visit), telephone calls and periodic inspection of the e-CRF with enough frequency to ascertain the following:

- Investigational medicinal product (IMP) storage conditions, sufficiency of drug supply for the trial.
- Compliance with approved protocol and all approved amendments, if any.
- That the investigator receives all documents and all trial supplies needed to conduct the trial properly and to comply with the applicable regulations.
- That the investigator and trial staff is adequately informed about the trial.
- Integrity and accuracy of data (as per monitoring plan):
 - i. Informed consent (version, signature and date)
 - ii. Eligibility criteria
 - iii. Baseline tests
 - iv. Adverse event collection
 - v. SAE and SAE reporting
 - vi. Biological samples storage and collection
 - vii. Drug stock reconciliation in pharmacy
- e-CRF completion
- Reporting of protocol deviations according GCPs and the applicable regulatory local requirements. Taking appropriate action to prevent recurrence to the detected deviations.

The study appointed CRO will review the e-CRFs for compliance with the protocol, and for inconsistent or missing data. Should any missing data or data anomalies be found, queries will be sent to the relevant center for resolution. Any systematic inconsistencies identified may trigger monitoring visits to centers. Following the required reviews, the e-CRF data items will be exported into the clinical study database for further analysis.

The onsite monitoring visits of the trial will be carried out by the CRO Sofpromed Investigación Clínica, SLU in Spain, and in some cases by duly appointed monitoring agents/partners in the other participating countries.

Monitoring visits will be done by qualified study monitors. It is understood that these monitors will have access to the clinical records after asking the investigators. Adequate time for these visits should be allocated by the investigators. The investigators will also ensure that the monitor is given direct access to the relevant documents.

When a monitoring visit is required, monitors will contact the center to discuss dates of proposed visit. Once a date has been confirmed, the center should ensure that the relevant patient source documents are available for monitoring.

If any problems are detected in the course of the monitoring visit, the study CRO (or the delegated agent/partner in the country) will work with the Principal Investigator to resolve issues and, if necessary, to determine the center's future participation in the study.

Monitors will review essential documentation and carry out source data verification to confirm compliance with the site agreement and trial protocol, and to ensure the protection of patients' rights as detailed in the Declaration of Helsinki 1964 (and its subsequent amendments).

11. STUDY DESIGN AND STATISTICS

11.1 Study design

GEIS-32 is a phase II, open-label, non-randomized, multicenter clinical trial with three strata (1-a typical SFT, 1-b malignant/dedifferentiated SFT and 2 EMC). The study will be developed at international level with 8 sites in Spain, 5 sites in Italy and 5 sites in France, during a recruitment period of 36 months. Patients will receive oral pazopanib at 800 mg once daily continuously. Patients will continue to receive treatment until there is evidence of progressive disease, unacceptable toxicity, non-compliance, withdrawn consent or investigator decision. The IMP will be investigated separately in the cohorts.

11.2 Study endpoints

Primary endpoints

- Objective response rate (ORR) (confirmed complete response [CR] and partial response [PR]), measured using Choi and RECIST 1.1 criteria. Response criteria will be based on the baseline identification of target lesions and follow-up until tumor progression.

Secondary endpoints

- Efficacy measured by the progression-free survival (PFS) rate assessed by median time
- Overall survival (OS) measured since treatment start date until date of death, whichever the cause.
- Clinical benefit rate (CBR). Patients who have reached CR, PR or SD during 6 months or more, presenting clinical improvement of symptoms, will be considered as having experienced clinical benefit.
- Long term safety profile of pazopanib, through assessment of adverse event type, incidence, severity, time of appearance, related causes, as well physical explorations and laboratory tests. Toxicity will be graded and tabulated by using NCI-CTCAE 4.0.

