	
For variables that follow binomial distributions (e.g. response rate) frequency and percentages will be calculated, together with their corresponding exact 95% confidence intervals. For time-to-event variables (e.g. PFS or OS) Kaplan-Meier estimations will be used. To analyze the reduction of risk and the influence of other variables on time-to-event variables Cox Regression will be applied. To correlate pharmacodynamics markers and biomarkers with clinical response standard methods for bivariate and multivariate regression and correlation will be used. Multivariate methods will be used only if the required assumptions are verified.

Analytical Endpoints
	
Primary endpoint
 
 • Objective response rate (ORR) (confirmed complete response [CR] and partial response [PR]), measured using Choi and RECIST 1.1 criteria. Response criteria will be based on the baseline identification of target lesions and follow-up until tumor progression. 
Secondary endpoints
 
 • Efficacy measured by the progression-free survival (PFS) rate assessed by median time. • Overall survival (OS) measured since treatment start date until date of death, whichever the cause. • Clinical benefit rate (CBR). Patients who have reached CR, PR or SD during 6 months or more, presenting clinical improvement of symptoms, will be considered as having experienced clinical benefit. • Long term safety profile of pazopanib, through assessment of adverse event type, incidence, severity, time of appearance, related causes, as well as physical explorations and laboratory tests. Toxicity will be graded and tabulated by using NCI-CTCAE 4.0.

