From a clinical point of view, studying the behavior of the tumor variants that are initially classified in the same groups, separately, will contribute to understanding the future treatments for the different variants.

Novel therapies are currently under development in soft tissue sarcomas, and in SFT. Sunitinib, sorafenib and the combination of temozolomide (TMZ) and bevacizumab (BEV) have demonstrated activity in the literature⁴. Fourteen patients with HPC/SFT who began treatment with TMZ/BEV at MDACC between the time period of May 2005 and June 2007 were analyzed⁵. The main reasons for starting treatment were: Symptomatic disease in 7 neoadjuvant treatments; disease recurrence/progression in 8 and 5 with new development of metastatic disease. Seven patients had metastatic disease at the time of initiation of treatment. The most common site of primary disease was the meninges. No patients had extremities as their primary disease. Eleven out of 14 patients achieved partial response (PR) by Choi criteria after starting TMZ/BEV therapy. PR was seen both as decrease in size, or in density. Best response assessment using conventional RECIST criteria, one patient had a RECIST PR. Median progression-free survival period for the entire group was 8.87 months. Median follow-up period for the group was 20 months. Sunitinib in a retrospective revision of Istituto Nazionale dei Tumori showed in 31 patients clinical benefit (PR+SD) > 60%⁶. Other similar experiences have been seen with sunitinib and sorafenib⁶⁻⁹, and some isolated with pazopanib¹⁰.

SFT has been related to hypoglycemic caused by paraneoplastic overexpression and secretion of high-molecular-weight insulin-like growth factor II¹¹. Additionally, the treatment with figitumumab, an anti-IGFR, has been successful, in combination with sunitinib, in one SFT progressive with sunitinib. On the other hand, it has been shown that most SFT have strongly activated PDGFR B, EGFR and IGFR (interdependency across receptors). The same authors found overexpression of AKTp and mTOR in more aggressive SFT subsets¹².

Interestingly, pazopanib has been related to growth suppression of synovial sarcoma through the inhibition of PI3K pathway¹³.

Extraskeletal Myxoid Chondrosarcoma (EMC)

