4. SELECTION OF PATIENTS

4.1 Inclusion criteria

1. Patients must provide written informed consent prior to performance of study-specific procedures or assessments and must be willing to comply with treatment and follow-up. Informed consent must be obtained prior to start of the screening process. Procedures conducted as part of the patient's routine clinical management (e.g. blood count, imaging tests, etc.) and obtained prior to signature of informed consent may be used for screening or baseline purposes as long as these procedures are conducted as specified in the protocol.
2. Age \geq 18 years or legal age of consent if greater than 18 years.
3. Histologic diagnosis of solitary fibrous tumor (stratum 1) or extraskeletal myxoid chondrosarcoma (stratum 2) (unresectable, locally advanced or metastatic disease) confirmed by central pathology review. Paraffin-embedded tumor tissue must be provided for all subjects for biomarker analysis before and (when feasible) after treatment with investigational product.
4. Patients with metastatic tumor suitable for complete resection can be recruited. In absence of progressive disease these patients should be treated with the study drug for at least 6 months.
5. For patients who have received previous anticancer treatments, progressive disease must be demonstrated within 6 months prior to enrollment.
6. Eastern Cooperative Oncology Group (ECOG) performance status of 0-2.
7. Measurable disease according to Choi (SFT) and RECIST 1.1 (EMC) criteria. Patients must have at least one measurable lesion (not in a previously irradiated area). If the only measurable disease is in a previously irradiated area, documented progression should exist after radiotherapy within the 6 months prior to enrollment.
8. Patients could have received a maximum of 4 lines of chemotherapy for metastatic disease prior to trial enrollment.
9. Patients must be able to swallow and retain the study drug.
10. Adequate organ system function as defined in the table below:

Table 1: Definitions for Adequate Organ Function

System	Laboratory Values
Hematologic	
Absolute neutrophil count (ANC)	$\geq 1.5 \times 10^9/L$
Hemoglobin ^a	$\geq 9 \text{ g/dL}$ (5.6 mmol/L)
Platelets	$\geq 100 \times 10^9/L$
Prothrombin time (PT) or international normalized ratio (INR) ^b	$\leq 1.2 \times \text{ULN}$
Activated partial thromboplastin time (aPTT)	$\leq 1.2 \times \text{ULN}$
Hepatic	
Total bilirubin	$\leq 1.5 \times \text{ULN}$

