7.9 Biological sample collection

Tumor block collection

A paraffin-embedded block will be collected during the screening period for central pathological review. First diagnosis sample or another more recent available sample obtained during the routine care previous to study entry will be acceptable. Tumor biopsy at study entry will not be compulsory but recommended if clinically acceptable (e.g. superficial or easily accessible locations). It is strongly recommended if the previous histological material of the patient stems from more than one year in cases with pauci-symptomatic disease or in any fast growth rate tumor, before enrollment. The main reason is that in some surgical series there were focal poorly differentiated areas (which could be absent in the shipped block) in cases that ultimately died after metastatic recurrence of the anaplastic component. A post-treatment tumor sample will be collected when possible (selected patients for whom post-treatment biopsy could be performed). Please see the translational research section for more details on tumor block collection.

Blood sample collection

Serum will be collected as described:

- Three 5-mL tubes within 72 hours prior to starting the treatment (baseline).
- Three 5-mL tubes within 72 hours after radiological response is documented.
- Three 5-mL tubes within 72 hours after progressive disease is documented.

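### The clinical benefit rate requires symptom improvement as well as tumour control, so patients without baseline symptoms can never count and the rate can fall below the response rate

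*Protocol*

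**What the plan says.** Section 11.2 lists CBR as a secondary endpoint and counts patients with "CR, PR or SD during 6 months or more, presenting clinical improvement of symptoms, will be considered as having experienced clinical benefit". The trial summary repeats the condition "presenting clinical improvement of symptoms", so this is not a slip in one place.

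The primary endpoint in the same section is "Objective response rate (ORR) (confirmed complete response [CR] and partial response [PR]), measured using Choi and RECIST 1.1 criteria". It carries no symptom condition and no 6-month condition.

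Other sections that bear on the definition:

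- **Entry.** Section 4.1 admits "Eastern Cooperative Oncology Group (ECOG) performance status of 0-2", and no criterion requires symptoms. Section 7.9 gives biopsy advice "in cases with pauci-symptomatic disease".
- **Denominator.** Section 11.4 puts every participant in the intent-to-treat efficacy analysis. CBR is not restricted to patients with symptoms at baseline.
- **Measurement.** Table 5 (section 7.1) schedules ECOG, physical examination, laboratory tests and imaging, but no symptom scale. Sections 7.6 and 11.5 have baseline tumour symptoms recorded as adverse events only when they become worse or more frequent. Improvement has no stated record.
- **Usage elsewhere.** Section 2.1 reports a retrospective sunitinib series that "showed in 31 patients clinical benefit (PR+SD) > 60" per cent, with no symptom condition.

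**The concern.** A clinical benefit rate is normally read as responses plus durable stable disease, so a reader expects it to be at least as high as the response rate. Here the symptom clause applies to every patient in the numerator, responders included. Someone with no symptoms at entry has nothing to improve and is scored as having no benefit whatever the tumour does.

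The result would then mix three things: tumour control, the share of patients who had symptoms at entry, and a judgement of improvement for which the protocol names no instrument, threshold or visit. The trial is open-label with a single treatment, and central imaging review cannot check that judgement. A low CBR could reflect a poor drug or a largely asymptomatic cohort, and the reported figure would not show which.

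**Working it through.** **Plan's own figure.** The protocol states no target, sample size or power for CBR, so there is no CBR figure to reproduce. The stratum 1-a rule borrowed below for the example (16 or more responses of 30, section 11.3) does reproduce. Exact binomial gives alpha 0.0971 at 40% and power 0.825 at 60%, within the stated 0.1 and 0.2.

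**Step 1, logic.** Under the text, the CBR numerator is (CR, PR or SD for 6 months or more) AND (symptoms improved). The ORR numerator is confirmed CR or PR. A responder whose symptoms do not improve, or who has none, counts for ORR and not for CBR. CBR below ORR is therefore possible.

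**Step 2, worked example, N = 30.** The 16 responders are the section 11.3 threshold; the 4 patients with SD of at least 6 months and the 10 with symptoms are assumed.

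- ORR = 16/30 = 53.3%.
- Without the symptom clause, CBR = (16 + 4)/30 = 66.7%.
- With the clause, if 10 of those 20 had baseline symptoms and all 10 improved, CBR = 10/30 = 33.3%.

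**Step 3, when CBR falls below ORR.** Let R be the ORR, D the share with SD of at least 6 months, s the share symptomatic at baseline and m the share of those who improve. Take all responses to last 6 months, and s and m to be equal in responders and SD patients. Then

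CBR = (R + D) × s × m, which is below R when s × m < R/(R + D).

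The protocol gives neither s nor m. The assumed ranges are s = 30–100% and m = 50–80%.

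| R | D | CBR without clause | CBR with clause | Below ORR if s × m is under |
|---|---|---|---|---|
| 60% | 20% | 80% | 12% to 64% | 0.75 |
| 40% | 30% | 70% | 10.5% to 56% | 0.571 |
| 20% | 50% | 70% | 10.5% to 56% | 0.286 |

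First row, lower end: 0.80 × 0.30 × 0.50 = 0.12. Upper end: 0.80 × 1.00 × 0.80 = 0.64.

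**Step 4, ceiling on CBR.** Let c be disease control (CR, PR or SD of at least 6 months), assumed to be 60%, and a the asymptomatic share, assumed to be 20%, 35% or 50%.

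- If control is equally frequent with and without symptoms, and every symptomatic controlled patient improves, CBR is at most c × (1 − a): 0.60 × 0.80 = 48%, 0.60 × 0.65 = 39%, 0.60 × 0.50 = 30%.
- With no such assumption, the hard cap is min(c, 1 − a): min(60%, 80%) = 60%, min(60%, 65%) = 60%, min(60%, 50%) = 50%.

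**Step 5, duration.** The 6-month wording can attach to SD alone or to CR and PR as well. On the second reading, responses shorter than 6 months are another way for CBR to fall below ORR, even without the symptom clause.

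**The case against.** The strongest reply is that the protocol deliberately chose a stricter composite, worded the same way in both places, and that a low value of a stricter endpoint is not bias. As a matter of intent that is fair. It does not explain why patients who cannot meet the symptom condition are kept in the denominator, or why no measure of improvement is scheduled.

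It can also be said that ECOG every 4 weeks and physical examinations carry some information, and that an SAP or e-CRF could define improvement. This stands in part. However, the protocol does not name ECOG as the criterion, and an SAP that dropped the clause would contradict the protocol.

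Several stronger readings are tempting but unsupported:

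- **A guaranteed loss of 12 to 30 points.** A reader might take 48%, 39% and 30% as firm maxima. They hold only if control is equally frequent with and without symptoms. Against the hard caps, the certain loss from 60% is 0, 0 and 10 points.
- **A failed benchmark.** Section 2.1 gives no duration for its figure above 60%, and the protocol does not name that series as a comparator for CBR. The 60% used here is an assumption.
- **Proof that asymptomatic patients will enrol.** Pauci-symptomatic means few symptoms, not none, and ECOG 0 is a performance grade. Such patients are eligible; their number is unknown.
- **A scan-timing error.** With 8-weekly scans, 6 months (about 26 weeks) falls between weeks 24 and 32. SD can simply be established at the later scan, so this needs a statement, not a correction.

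**Conclusion.** The definition is flawed as written. A patient without baseline symptoms can never count towards CBR, even with a durable complete response, and CBR can be lower than ORR. Both follow from the text, and no other section cures them. The direction is certain, because the clause can only remove patients from the numerator.

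The size is not known. The 33% against 53% is one example resting on assumed numbers, and the general understatement depends on the symptomatic share and on how many of those patients improve.

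A reader might infer that the trial's conclusions are at risk. They are not: CBR has no hypothesis, threshold or stopping role, and every decision rule in section 11.3 uses ORR. Severity is minor to moderate.

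**What to change.** In section 11.2 and the trial summary, define CBR as the proportion of all intent-to-treat patients with confirmed CR or PR, or with SD lasting at least 6 months. State that the duration applies to SD, and name the scheduled scan that establishes it. Delete the symptom clause.

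Symptom improvement may be kept as a separate descriptive item among patients symptomatic at baseline, provided that a measure and its visits are named.

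Cost: one definition reworded in two places. The revised CBR needs no new data, since response, stability and duration already come from the 8-weekly scans. The separate symptom item is not free, because its measure would have to be specified and collected. The downside is that CBR loses its symptomatic component.
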